- 19
- 20
- 21
- 22
- 23
- 24
- 25
- 26
- 27
- 28
- 29
- 30
- 31
- 32
- 33
- 34
- 35
- 36
- 37
- 38
- 39
- 40
- 41
- 42
- 43
- 44
- 45
- 46
- 47
- 48
- 49
- 50

B5.3 Research Procedures

Study Design

Following a 10-hr overnight fast, a baseline blood draw will be conducted. A baseline muscle biopsy, obtained from the lateral portion of the vastus lateralis, will be collected under local anesthetic (lidocaine). Participants will rest for 15-min before beginning a 5-min warm-up on a cycle ergometer at 50% peak power output (determined from screening $VO_{2\text{peak}}$ test). A glycogen depletion protocol (38) will then be initiated with participants cycling at various intensities until failure. A second muscle biopsy will be performed immediately after completion of glycogen depletion. This biopsy will allow for confirmation of glycogen depletion and allow for the assessment of the initial impact of exercise-induced glycogen depletion on microRNA expression. Participants will then consume a carbohydrate (CHO: $1 \text{ g}\cdot\text{kg}^{-1}\cdot\text{hr}^{-1}$) or an energy free control (CON) beverage matched for taste and color during the first 3-hr post glycogen depletion. Blood will be drawn from a catheter every 30-min post-exercise to assess changes in serum glucose and insulin. At 3-hr post-exercise a third muscle biopsy will be conducted to assess acute effects of carbohydrate consumption on microRNA during the initial phase of glycogen resynthesis during the early phase recovery from exercise. For the remainder of the day participants will consume meals ready-to-eat (MRE) components designed to adequately or inadequately replenish glycogen stores. On the study day in which participants receive the carbohydrate beverage, daily intake will be provided as $6.0 \text{ g}\cdot\text{kg}^{-1}$ carbohydrate, $1.2 \text{ g}\cdot\text{kg}^{-1}$ protein, $1 \text{ g}\cdot\text{kg}^{-1}$ fat. On the study day in which participants receive the placebo beverage, daily intake will be provided as $1.5 \text{ g}\cdot\text{kg}^{-1}$ carbohydrate, $1.2 \text{ g}\cdot\text{kg}^{-1}$ protein, $3.0 \text{ g}\cdot\text{kg}^{-1}$ fat. Following a 10-hr overnight fast, participants will return to the laboratory for a fourth muscle biopsy. As 24-hrs is sufficient time to replenish glycogen stores (1), the fourth muscle biopsy with modified daily carbohydrate intake will allow for isolation of the effect of carbohydrate availability on microRNA expression. Volunteers will then complete 80-min of steady-state ($\sim 60\%$ $VO_{2\text{peak}}$) cycle ergometry consuming carbohydrate at a rate of $1.8 \text{ g}\cdot\text{min}^{-1}$ enriched with U- ^{13}C -glucose and U- $^{13}\text{C}_6$ -D-fuctose to determine exogenous carbohydrate efficiency. A final biopsy will be taken at the conclusion of the exercise bout. This fifth biopsy will be conducted to assess the impact of initiating steady-state exercise with adequate or low glycogen stores on molecular markers of glucose uptake and substrate utilization. Following a minimum 7-d washout period volunteers will return to the laboratory to complete the second arm of the investigation. To ensure glycogen stores are similar between volunteers on testing day, 48-hrs prior to testing all volunteers will complete a glycogen depletion protocol and then consume a diet providing $6.0 \text{ g}\cdot\text{kg}^{-1}$ carbohydrate to replenish glycogen stores.

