17 exertional syncope) or shows signs of poor perfusion, or if there is an equipment failure.
18

19 Muscle Biopsy

20 Percutaneous muscle biopsy will be performed to obtain skeletal muscle samples for assessment of
21 muscle glycogen, microRNA expression and molecular pathways regulating carbohydrate metabolism.
22 Muscle samples will be taken from the vastus lateralis using a 5-mm Bergstrom needle with manual suction
23 while the participant is under local anesthesia (1% lidocaine) according to the approved USARIEM SOP
24 (42, 43). Multiple passes with the biopsy needle may be necessary to obtain adequate sample with each
25 biopsy. Muscle biopsies will be conducted immediately before and after the muscle glycogen depletion
26 protocol. After the second muscle biopsy volunteers will rest and consume either a carbohydrate beverage
27 or a matched placebo. Three hours following the conclusion of the glycogen depletion protocol a third
28 biopsy will be obtained to assess the acute influence of carbohydrate intake. Volunteers will be allowed to
29 leave at this point. Volunteers will return the following morning for a fourth muscle biopsy taken at a new
30 incision site. In this same incision a fifth biopsy will be taken after 80-min of steady state exercise to
31 determine the influence of adequate or low glycogen storage on exogenous carbohydrate uptake and
32 oxidation during exercise. Following a minimum 7-d washout period, volunteers will return to the laboratory
33 to complete the second arm of the investigation. A total of ten muscle biopsies will be conducted per
34 volunteer.
35

36 Assessment of Resting Respiratory Quotient

37 Respiratory Quotient (RQ) will be measured under resting conditions before the 24-hr post glycogen
38 depletion muscle biopsy, using open circuit indirect calorimetry (Parvo Medics). Assessment of RQ will
39 allow us to determine the influence of glycogen storage on carbohydrate and fat oxidation. Measurements
40 will occur between 0500-0800-hrs following a minimum 10-hr overnight fast. Volunteers will rest in the
41 supine position for approximately 30-min prior to each measurement in a quiet and dim, temperature
42 regulated room. To minimize error, volunteers will be instructed to minimize movement once the
43 mouthpiece is inserted, or the mask/hood is placed over their heads to collect expired air. The test will be
44 discontinued when 10-min of steady state oxygen consumption (VO_2) and carbon dioxide production

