45 (VCO_2) are recorded.
46

47 Steady-State Exercise

48 After the fourth muscle biopsy volunteers will complete 80-min of steady-state exercise on the cycle
49 ergometer at $60 \pm 5\%$ of their $VO_{2\text{peak}}$. During exercise VO_2 and VCO_2 will be measured for 4-min using a
50 metabolic cart (Parvo Medics) at approximately 0, 15, 30, 45, 60, and 75-min to determine substrate
51 oxidation. HR (measured continuously; Polar Electro) will be recorded at the same times as the metabolic
52

1 cart measurements. Breath samples will be collected at approximately 0, 20, 40, 50, 60, 65, 70, 75, and 80-
 2 min to determine exogenous carbohydrate oxidation using single-patient breath collection bags (Quin-Tron
 3 Instrument Company, Milwaukee, WI, USA). Breath will be transferred to 20 mL evacuated tubes.
 4

5 **Carbohydrate Supplementation**

6 After the post glycogen depletion muscle biopsy, volunteers will drink a CHO (glucose and fructose in a 2:1
 7 ratio) or CON beverage (Combat Feeding, Natick, MA). Carbohydrate will be provided at $1 \text{ g} \cdot \text{kg}^{-1} \cdot \text{hr}^{-1}$ in
 8 accordance with current American College of Sports Medicine Guidelines (40). The CON beverage will be
 9 sugar free and void of other nutrients to allow for assessment of the independent effect of carbohydrate
 10 availability on skeletal muscle and circulating microRNA expression. Beverages will be consumed
 11 immediately following the post glycogen depletion muscle biopsy and then every 30 min thereafter (5
 12 times) until the 3-hr post glycogen depletion muscle biopsy.
 13

14 Additionally, all participants will consume the CHO beverage at $1.8 \text{ g} \cdot \text{min}^{-1}$ during steady-state exercise to
 15 examine the impact of glycogen availability on exogenous carbohydrate oxidation efficiency. Volunteers
 16 will consume the beverage immediately before the start of the exercise and then again at 20, 40, and 60-
 17 min during the exercise bout. The CHO beverage consumed during exercise will be enriched with 200 mg
 18 of U- ^{13}C -glucose and U- $^{13}\text{C}_6$ -D-fructose (Cambridge Isotope Laboratory, Andover, MA, USA) to significantly
 19 increase the isotopic enrichment above natural levels and optimize the measurement of exogenous
 20 carbohydrate oxidation.
 21

22 **B5.4 Data Collection**

23 **Blood Sampling**

24 Blood samples will be collected using intravenous access by a USARIEM credentialed phlebotomist on

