Following identification of skeletal muscle microRNA that had a significant change, Taqman® probes (Applied Biosystems) will be used to assess the expression of these microRNA in serum to determine their potential use as noninvasive markers of altered carbohydrate metabolism following glycogen depletion and repletion. Total circulating miRNA will be extracted from 200 μ L serum using miRNeasy Serum/Plasma kit, which allows for extraction and purification of small (< 200 nt) cell-free RNA (Qiagen, Valencia, CA, USA). Exosomal circulating miRNA will also be extract from 1000 μ L serum using miRCURY™ RNA Isolation Kit to measure miRNA. To avoid introduction of potentially contaminating material, prior to RNA extraction serum samples will be centrifuged for 10 min at 4°C to remove cellular debris. Supernatant will be removed and transferred to a new tube without disturbing the pellet. Due to the small amount of RNA in the serum, 3.5 μ L of a Spike-In Control (C. elegans miR-39; Qiagen) will be added to all samples prior to extraction of RNA to determine the yield of template recovered. After extraction 3 μ L of serum RNA will be reverse transcribed using the TaqMan® microRNA RT kit (Applied Biosystems) with miRNA-specific stem-loop RT primers pooled in 1X-Tris-EDTA (TE) buffer for a final dilution of 0.05X. A pre-amplification step will be performed after reverse transcription to increase cDNA template using a primer pool of 20 X Taqman® Small RNA Assays (Applied Biosystems) for miRNA of interest at 0.05X concentration in 1X TE buffer. All serum miRNA will be normalized to the geometric of external (Spike-In Control C. elegans miR-39) and internal controls to allow for both technical and inter-individual normalization (47). Geometric mean of controls will be used to correct for possible outlying values and abundance differences between the different controls (48).

All reverse transcription for mRNA and miRNA, and pre-amplification of serum miRNA will be conducted in a T100™ Thermal Cycler (Bio-Rad, Hercules, CA). A StepOnePlus™ real-time PCR system (Applied Biosystems) will be used to perform all mRNA and miRNA analysis. Fold changes will be calculated using the $\Delta\Delta C_T$ method as described below in statistical analysis section.

Bioinformatics Analysis

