32 Hard copy data records will be stored for a minimum of three years from the time the study is completed.
33 Electronic data records will be maintained for a period of at least five years after the study has been
34 completed.
35

36 **B5.6 Managing Data and/or Human Biological Specimens for Future Research**

37 Any use of the samples outside of this defined protocol will be submitted as a protocol amendment or a
38 new protocol. Samples will be retained for future analyses once the protocol is closed if the subject
39 provided permission in the informed consent document.
40

41 **B5.8 Statistical Analysis**

42 **B5.8.1 Sample Size Estimation**

43 Statistical power and sample size were determined using the minimum fold change required for a
44 physiologically relevant difference in microRNA expression. Variance (standard deviation) was based
45 on recent publications assessing change in microRNA expression in skeletal muscle (18, 50, 51) and
46 circulating (34, 35, 52) in response to an acute bout of exercise. Using this information the sample
47 size necessary to determine statistical significance between intervention arms, with a mean fold
48

1 change of 1.5 ± 1 is 9 per group, with an alpha of 0.05 and 80% power. In the present study, 12
2 volunteers will be studied in a repeated measures crossover design to account for potential greater
3 inter-individual variability.
4

5 **B5.8.2 Data analysis**

7 Statistical analyses will be conducted using either SPSS (IBM Corp. Armonk, NY), SAS 9.3 (SAS
8 Institute Inc., Carey, NC), or equivalent. Common descriptive statistics will be used to describe
9 volunteer characteristics. Shapiro-Wilk tests will be used to determine normality of data. Mixed
10 model repeated measures ANOVA will be performed to determine main effects of time (baseline,
11 immediately, 3-hr, and 24-hr post glycogen depletion), carbohydrate intake ($6.0 \text{ g} \cdot \text{kg}^{-1} \cdot \text{d}^{-1}$ versus $1.5 \text{ g} \cdot \text{kg}^{-1} \cdot \text{d}^{-1}$) and time-by-carbohydrate interactions for skeletal muscle and circulating microRNA, mRNA
12 expression, and markers of nutritional status. If interactions are significant, Bonferroni correction will
13 be used to examine these relationships. Correlation coefficients and multiple regression analysis will
14 be used to evaluate relationships between study outcome measures. The alpha level will be adjusted

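### The carbohydrate-versus-control contrasts at 3 h and 24 h should be pre-specified and not wait on a significant interaction; what the condition costs depends on an outcome scale that the plan leaves open

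*Combined protocol and SAP*

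**What the plan says.** - **Role of the biopsies (B5.3, Study Design).** The second biopsy confirms depletion. For the third: "At 3-hr post-exercise a third muscle biopsy will be conducted to assess acute effects of carbohydrate consumption on microRNA". For the next morning: "the fourth muscle biopsy with modified daily carbohydrate intake will allow for isolation of the effect of carbohydrate availability on microRNA expression".
- **When the arms diverge (B5.3, Muscle Biopsy and Carbohydrate Supplementation).** "After the second muscle biopsy volunteers will rest and consume either a carbohydrate beverage" or the placebo. The drinks are taken "immediately following the post glycogen depletion muscle biopsy and then every 30 min thereafter (5" times). The baseline and immediately-post samples therefore precede any difference between arms.
- **Model (B5.8.2).** A mixed "model repeated measures ANOVA will be performed to determine main effects of time (baseline", immediately post, 3 h and 24 h), of carbohydrate intake, and of their interaction. No period or sequence term is listed.
- **Follow-up (B5.8.2).** "expression, and markers of nutritional status. If interactions are significant, Bonferroni correction will" be used. Neither the contrasts nor their number is given. A general sentence adds that alpha will be adjusted for multiple comparisons.
- **Scale (B5.4, mRNA and microRNA Expression).** Fold changes are to come from the delta-delta-CT method and the reader is referred to the statistical section, but B5.8 does not describe it. The reference sample is not stated.
- **Serum step (B5.4).** Serum assays follow "Following identification of skeletal muscle microRNA that had a significant change"; that term is not defined.
- **Order.** "Following a minimum 7-d washout period volunteers will return to the laboratory to complete the second arm of the investigation". Diet Intervention says the order is randomised; no blocking or ratio is stated. B5.2.2 continues until 12 volunteers have complete data.

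**The concern.** The two contrasts that B5.3 relies on are the ones the analysis reaches last. The carbohydrate test that needs no prior result is the main effect, and it mixes in two samples in which no arm difference can be expected. If it were quoted as the carbohydrate effect, it would understate that effect and could not separate the acute question from the next-day one. The 3-hr and 24-hr contrasts do separate them, but they are described only once a 3-df interaction has passed 5%. Two contrasts with Bonferroni already hold the joint error at 5%, so the extra condition makes them harder to reach than their own error rate requires. A secondary issue is that this is a two-period crossover with no period term listed and no stated balance of order.

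**Working it through.** **1. The plan's own figure.** B5.8.1 gives 9 per group for 1.5 ± 1, alpha 0.05, 80% power. A two-sided two-sample t-test (sidedness assumed) with d = 1.5/1 needs n = 8.06, rounded up to 9; power is 79.7% at 8 and 84.8% at 9. The figure reproduces. It sizes one direct comparison between arms, not a contrast reached through an interaction test.

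**2. What the main effect estimates.** The expected arm differences at the four times are (0, 0, d3, d24), so the main effect is (0 + 0 + d3 + d24)/4. If d3 = d24 = d this is d/2; if only one time responds it is d/4.

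**3. Set-up for power.**
- From the documents: n = 12, alpha 0.05, four times. The interaction has 4 − 1 = 3 and 3 × 11 = 33 df.
- Assumed, because the documents do not give them: SD 1 per sample within a person; a share r of that variance common to a test day, with r = 0, 0.25 or 0.5; normal errors; 6:6 order with a period term; two contrasts at 0.025 each, with and without the condition.

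The arm difference at one time has variance 2, of which 2(1 − r) is not shared across times.
- Interaction noncentrality = 12 × Σ(d_t − mean d)² / [2(1 − r)]. For 1.0 at both times the sum is 4 × 0.5² = 1, giving 6/8/12 and power of about 47/60/79%. For 1.0 at one time the sum is 0.75² + 3 × 0.25² = 0.75, giving 4.5/6/9 and about 36/47/65%.
- Standard error of a raw-scale contrast: √(2/12) = 0.41 at every r.
- Standard error relative to same-visit baseline: √(4(1 − r)/12) = 0.58/0.50/0.41.

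A baseline-referenced contrast is itself part of the interaction, so the two tend to be significant together. A raw contrast also uses the between-day comparison, which the interaction ignores. That is why the condition costs more on the raw scale.

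**4. Power for at least one of the two contrasts** (simulation, r = 0/0.25/0.5; repeat runs agree to about a point):

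| True effect | Scale | With condition | Without |
|---|---|---|---|
| 1.0 SD, both times | raw | 45/52/59% | 79/75/68% |
| 1.0 SD, one time | raw | 33/38/44% | 56/56/54% |
| 1.5 SD, both times | raw | 84/92/95% | 99/98/96% |
| 1.0 SD, both times | vs baseline | 35/47/67% | 42/53/70% |
| 1.0 SD, one time | vs baseline | 24/33/51% | 30/39/56% |
| 1.5 SD, both times | vs baseline | 73/85/96% | 76/87/97% |

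At 1.0 SD the loss is 9 to 34 points on the raw scale and 3 to 7 relative to baseline. At 1.5 SD at both times (the planning figure read as the arm difference) it is 1 to 15 and 0 to 3 points.

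**5. Type I error.** Joint error per microRNA is about 1-3% with the condition and just under 5% without it. If a significant main effect or interaction counts as detection, power at 1.0 SD at both times is about 79/76/85%, with about 10% type I error and no attribution to a time.

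**6. Period.** If the second visit shifts values by s, the unadjusted raw-scale estimate is off by s × (n1 − n2)/12. That is 0 at 6:6, 4/12 = one third of s at 8:4, and 6/12 = half of s at 9:3. Under simple randomisation (assumed), P(6:6) = 924/4096 = 22.6% and P(9:3 or worse) = 598/4096 = 14.6%. Averaged over randomisation the bias is zero. An additive shift cancels in the interaction and in any value relative to same-visit baseline.

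**The case against.** The strongest reply is that the large power gaps belong to the raw scale, while B5.4 speaks of delta-delta-CT fold changes. If same-visit baseline is the reference, the condition costs at most about 7 points and an additive period shift drops out. This stands, and it limits the size of the point. It does not settle it: the reference sample is not stated, and muscle microRNA is first measured by sequencing, for which no analysis scale is given.

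Other parts also stand. Objective 1 in B4 covers depletion as well as repletion; the time effect serves depletion, so the four-time model is appropriate. The interaction is a valid test that the arms diverge. With many sequenced microRNA, a conservative screen is a defensible choice, although the adjustment across microRNA that B5.8.2 already promises is the more direct tool.

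Three stronger readings are tempting and are not supported:
- A reader might infer that responsive microRNA will be lost before the serum assays. Because B5.4 does not define a significant change, a main effect or interaction alone may count, and then the plan detects about as much at 1.0 SD at both times. Loss is possible, not shown.
- A reader might infer that the plan will report a halved effect. B5.8.2 does not say that the main effect will be quoted as the carbohydrate effect.
- A reader might infer that omitting the period term biases the trial. Order is randomised, so there is no bias on average, and practice rides, standardised depletion and diet, and washout make a large shift less likely.

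**Conclusion.** The plan should be changed, but the flaw does not invalidate it. B5.3 sets two time-specific carbohydrate questions, and B5.8.2 neither names the matching contrasts nor lets them be tested without a significant interaction. Under the assumptions above (n = 12, SD 1 per sample, day-level share 0 to 0.5, two contrasts), an effect of 1.0 SD loses 9 to 34 points of power on the raw scale and 3 to 7 points relative to same-visit baseline. The raw-scale figures should not be presented as the plan's loss, because the documents leave the scale open. At 1.5 SD at both times the loss is small except on the raw scale with no day-level correlation (15 points). The period and balance issue is secondary: it costs power, or biases the realised estimate at an unequal split, only if a period shift exists and values are not baseline-referenced.

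**What to change.** In B5.8.2:
- Keep the four-level time model for the depletion question. Fit time, arm, time-by-arm and a fixed period effect, with participant and visit-within-participant random effects.
- Pre-specify two carbohydrate-versus-control contrasts from this model, at 3 h and at 24 h, with Holm or Bonferroni over the two and not conditional on the interaction.
- State whether the contrasts are on the raw or the baseline-referenced scale, and name the delta-delta-CT reference sample.
- Apply the promised multiplicity adjustment across microRNA on top of this.
- Report the interaction as supporting evidence and the four-time carbohydrate main effect as descriptive.

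In B5.4, define which result counts as a significant change for the serum step. In B5.3, allocate order 6:6 in blocks, with a replacement taking the order of the person replaced.

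The cost is plan wording, model code and an allocation list; no new samples are needed. Joint type I error per microRNA rises from about 1-3% to the nominal 5%. With no period shift, the period term costs about 1 point of power at 6:6. For a single paired contrast it takes 80% to 74% at 8:4 and 67% at 9:3, which is the reason for balanced blocks.

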 25 glycogen protocol days at baseline (before glycogen depletion), immediately following and every 30 min
 26 after the glycogen depletion protocol to assess circulating glucose and insulin (**Figure 1**). Baseline and 24-
 27 hr post glycogen depletion blood sampling will occur after a 10-hr overnight fast. A total of 120 mL of blood
 28 will be sampled from each volunteer during each glycogen depletion protocol day study (**Table 2**). Blood
 29 samples will be used to assess nutrient status (glucose and insulin) and circulating microRNA.
 30

31 Biochemical indices of metabolic homeostasis will be measured from stored samples at USARIEM.
 32 Unused serum will be retained for future use if subject provide permission in the informed consent
 33 document. Samples will be stored at USARIEM using subject identification numbers.
 34

35 **Table 2. Volume of Blood Sampled for Glycogen Protocol Day**

Tube	Number of Tubes	Total Volume (mL)
10 mL Red Top Tube	5	50
7 mL Red Top Tube	10	70
Total	15	120

37 **Breath Sample Processing for Isotopic Enrichment**

38 Measurement of $^{13}\text{C}/^{12}\text{C}$ in expired CO_2 will be measured using isotope-ratio mass and cavity ring-down
 39 spectroscopy (Metabolic Solutions, Inc., Nashua, NH).
 40

41 **Calculations of Carbohydrate and Fat Oxidation**

42 Fat and CHO oxidation will be calculated from VO_2 and VCO_2 measured using open circuit indirect
 43 calorimetry (4 min collection), neglecting the contribution of protein oxidation to the energy yield (44):
 44

45
$$\text{Fat oxidation (g/min)} = 1.695 \times \text{VO}_2 \text{ (L/min)} - 1.701 \times \text{VCO}_2 \text{ (L/min)}$$

1 Glucose oxidation (g/min) = $4.585 \times VCO_2 \text{ (L/min)} - 3.226 \times VO_2 \text{ (L/min)}$

2

3 *Calculations of Exogenous and Endogenous Glucose Oxidation*

4 Exogenous glucose oxidation can be calculated:

5

6 Exogenous glucose (g/min) = $VCO_2 \times [(Rexp - Rref)/(Rexo - Rref)]/k$

7

8 where VCO_2 is in L/min, $Rexp$ is the observed isotopic composition of expired CO_2 , $Rref$ is the isotopic
9 composition of expired CO_2 at rest before ingestion of the first dose of ^{13}C -glucose and U- $^{13}C_6$ -D-fructose,
10 $Rexo$ is the isotopic composition of the exogenous glucose ingested, and k (0.747 L/g) is the volume of
11 CO_2 provided by the complete oxidation of glucose. Endogenous glucose oxidation can be calculated by

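### The four time levels in B5.8.2 leave the 30 to 150 min glucose and insulin samples out of any stated arm comparison

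*Combined protocol and SAP*

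**What the plan says.** B5.3 (Study Design) gives the purpose of the serial samples: "Blood will be drawn from a catheter every 30-min post-exercise to assess changes in serum glucose and insulin". The carbohydrate or control drink is a "beverage matched for taste and color during the first 3-hr post glycogen depletion".

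B5.4 (Blood Sampling) repeats the schedule. Blood is taken on "glycogen protocol days at baseline (before glycogen depletion), immediately following and every 30 min" "after the glycogen depletion protocol to assess circulating glucose and insulin", and a fasted 24-hr sample is also named. It adds that the "samples will be used to assess nutrient status (glucose and insulin) and circulating microRNA".

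B5.8.2 then describes a single mixed "model repeated measures ANOVA will be performed to determine main effects of time (baseline", "immediately, 3-hr, and 24-hr post glycogen depletion"), carbohydrate intake and their interaction. The outcomes are skeletal muscle and circulating microRNA, mRNA "expression, and markers of nutritional status". The only other inferential analysis is a general sentence on correlation and multiple regression, which names no variables, times or summary measures. No area under the curve, peak or separate time factor is given for glucose or insulin.

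**The concern.** The four levels match the first four biopsies, so they suit the muscle outcomes. They do not match the glucose and insulin series, which is denser by design.

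Under B5.3 and B5.4 (Carbohydrate Supplementation is described in B5.3), the first drink follows the post-depletion biopsy and further drinks follow every 30 min until the 3-hr biopsy. The immediate sample should therefore precede the drink. The 24-hr sample is fasted and comes after a day on different diets. Of the four levels, only 3-hr can show the response to the drink, and it shows only the end of it.

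Two things are at stake. The rise and fall of glucose and insulin during drinking, which is the direct readout of the randomised beverage, would not be compared between arms. And because no summary is prespecified, a peak, an area or a single time could be chosen after the data are seen.

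**Working it through.** **Count of draws per arm.** From B5.3 and B5.4: baseline (1), immediately after depletion (1), 30, 60, 90, 120, 150 and 180 min (6), 24-hr (1). Total 1 + 1 + 6 + 1 = 9. The 180 min end of the series is inferred from the 3-hr drinking period and the 3-hr biopsy.

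**Match to the model.** Baseline, 0 min, 180 min and 24-hr match a level (4). The 30, 60, 90, 120 and 150 min draws do not (5). Over 2 arms and 12 completers that is 5 × 2 × 12 = 120 of 9 × 2 × 12 = 216 listed samples.

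**Check against the plan's own figure.** C2 states 10 draws per protocol day, 20 in total; 20 × $35 = $700 agrees with the sum given there. The text lists 9, so the stated 10 is not reproduced. The tenth may be in Figure 1, which is not shown. If it lies outside the four levels (an assumption), the gap is 6 of 10.

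**What the extra samples could add.** The documents give no SD or effect size for glucose or insulin; B5.8.1 concerns microRNA only. The following is therefore illustration. Assumptions:
- 12 pairs, paired t-test, two-sided alpha 0.05.
- The within-person arm difference has the same SD (set to 1) at each time and a common correlation rho between times.
- Its mean is 0 at 0 min (before the drink) and 0.6 SD at each of the six later times.

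The trapezoidal area over seven equally spaced times, divided by its length, has weight 1/12 at each end and 1/6 at the five interior times.
- Raw area: mean = 0.6 × 11/12 = 0.55. Sum of squared weights = 2/144 + 5/36 = 0.1528. Variance = rho + (1 − rho) × 0.1528.
- Incremental area, with the 0-min value subtracted: the 0-min weight becomes −11/12. Mean = 0.55. Sum of squared weights = 121/144 + 5/36 + 1/144 = 0.9861. Variance = (1 − rho) × 0.9861.
- 3-hr value alone: standardised effect 0.6 at any rho.
- Change from 0 min to 3-hr: standardised effect 0.6 / sqrt(2(1 − rho)).

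| Analysis | rho 0.3: effect (power) | rho 0.5: effect (power) | rho 0.7: effect (power) |
|---|---|---|---|
| 3-hr value alone | 0.600 (47%) | 0.600 (47%) | 0.600 (47%) |
| Raw area, 0-180 min | 0.862 (78%) | 0.724 (63%) | 0.637 (52%) |
| Change, 0 min to 3-hr | 0.507 (36%) | 0.600 (47%) | 0.775 (69%) |
| Incremental area from 0 min | 0.662 (55%) | 0.783 (70%) | 1.011 (89%) |

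Each area does better than its single-time counterpart at all three correlations. The raw area gains least when rho is high. The power of the incremental area rises with rho, as does that of the simple change. No single gain can be quoted.

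**The case against.** The strongest reply is that absence from a listed time factor is not the same as being unused. B5.3 and B5.4 state why the samples are taken, and the correlation and regression sentence in B5.8.2 could draw on them. That is fair, and a reader should not infer that the samples will go unanalysed. The sentence does not close the gap, however: it names no variable, time or summary, and it does not compare the arms.

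Second, neither objective and neither hypothesis in B4 names glucose or insulin concentration. They concern microRNA, exogenous carbohydrate efficiency and phosphorylation of IRS-1 and AMPK. This stands. A reader might infer that the main conclusions or the sample size are weakened; the documents do not support that, because nothing in B5.8.1 rests on glucose or insulin.

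Third, a reader might want a definite power gain. None is available. The 0.6 SD is assumed, and the contrast is between carbohydrate and an energy-free drink, so the true difference could be much larger: at 1.2 SD the 3-hr value alone would have 97% power. A volume of blood attached to the unmodelled draws would be equally unsupported, since Table 2 does not assign tubes to times.

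Fourth, an area under the curve alone would hide the time course. This also stands, and is why the area should be added to a model with all times and not replace it.

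**Conclusion.** The point holds as a minor one. As written, B5.8.2 compares arms on glucose and insulin at four times and leaves out 5 of the 9 draws listed per arm, all from inside the drinking period. The count rests on the 30-min series ending at 180 min, and on the text schedule, which is one draw short of C2.

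How much is lost is not known. Under the illustrative assumptions, power is 47% for the 3-hr value alone, against 52% to 78% for the raw area and 55% to 89% for the incremental area, across rho 0.3 to 0.7. These figures also assume the same arm difference at every time after the drink starts; they show direction and spread and do not estimate this trial's gain. The case for the change is that the data will exist, were scheduled for this purpose, and have no stated arm comparison.

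**What to change.** In B5.8.2, for glucose and insulin only:
- Use every sampled time as a level of the time factor in the existing time-by-carbohydrate mixed model (nine levels on the text schedule).
- Prespecify one summary, the 0-180 min area under the curve, compared between arms within person. Say whether it is raw or incremental and, if incremental, fix the reference in advance, for example the pre-drink 0-min sample.

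Keep the four levels for skeletal muscle and circulating microRNA and for mRNA. While editing, reconcile the nine draws listed in B5.3 and B5.4 with the ten in C2, so that the time levels are complete.

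The cost is a sentence or two in B5.8.2. No new sample, visit or volunteer is needed, because the draws are already scheduled.
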